## 2 INTRODUCTION

### 2.1 STUDY RATIONALE

The purpose of the study is to evaluate the safety, tolerability, immunogenicity, and pharmacokinetics (PK) of single ascending intravenous (IV) doses of XTMAB-16 in healthy adult subjects. This study is the first time that XTMAB-16 will be administered to humans. The safety, tolerability and PK results obtained from this study will inform future clinical development of XTMAB-16 for the treatment of sarcoidosis.

XTMAB-16 is being developed as a monoclonal antibody (mAb) tumor necrosis factor alpha (TNF $\alpha$ ) blocker to address the treatment gap for patients with advanced pulmonary sarcoidosis with or without extrapulmonary involvement.

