In a 13-week, repeated dose, GLP, toxicology study (Study 14042-20005) in hTNF $\alpha$  transgenic mice, KBMAB-16 was well tolerated up to 40 mg/kg after 7 bi-weekly IV injections in TgTC animals in the toxicity study with no meaningful test article related clinical and pathological abnormalities observed. The NOAEL of KBMAB-16 was considered to be 40 mg/kg after 7 doses biweekly IV injection in TgTC mice. In addition, safety pharmacology assessments of the central nervous system (CNS) and respiratory systems did not reveal adverse effects at any dose of KBMAB-16. After 40 mg/kg IV injection for 6 doses, the  $C_{max}$  was 1104.9  $\mu$ g/mL, the  $(AUC)_{0-\infty}$  was 624865.9  $\mu$ g\*hr/mL and the  $(AUC)_{0-\tau}$  was 124878.7  $\mu$ g\*hr/mL. The systemic exposure in terms of  $C_{max}$  and  $(AUC)_{0-\infty}$  increased in a dose proportional manner in the dose range from 10 to 40 mg/kg of KBMAB-16.

For further detailed nonclinical data for XTMAB-16, refer to the IB.

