#### 4.1.1 DOSE ESCALATION

For all cohorts, a sentinel group of 2 participants (1 assigned to XTMAB-16 and 1 assigned to placebo) will be dosed at least 48 hours before the remaining participants in the same cohort. After blinded review of the available safety and laboratory data by the PI, if no notable safety signals are identified, the remaining participants within the same cohort will be dosed.

Participants within a cohort should be dosed at least 1 hour apart.

As XTMAB-16 is a TNF $\alpha$  inhibitor, which have well-characterized clinical safety profiles, it can be given to participants in the 4 mg/kg dose group after 14 to 21 days clinical assessment of the participants at 2 mg/kg dose group, unless safety concerns arise.

Dose escalation will be stopped as soon as safety signals or risks are identified or anticipated, based on:

- Number of abnormal and clinically significant safety laboratory results
- Number of SAEs and/or TEAEs with severity/intensity high enough for a meaningful decision
- Proportion of TEAEs of the same type high enough to justify the decision

The severity rating is adapted to healthy participants, taking into account event characteristics such as type, deleterious potential, occurrence, progression, and monitorability. A solitary SAE occurrence is not by itself a criterion for making a decision (assessment depends on the nature of the reported event). See Section 4.1.2 for details on stopping rules.

A decision to proceed from dose “n” to the next higher “n+1” dose will be made jointly by the Sponsor and the Investigator based on a preliminary Investigator blinded safety report inclusive of the 12 participants in dose level cohort “n”. The relevant data for this decision should be, at a minimum, AEs, liver and kidney function tests, ECG, blood pressure, and heart rate.

For safety purposes, the treatment of a specific participant may be unblinded before the next dose level is administered, after mutual agreement between the Sponsor and the Investigator.

An unscheduled PK sample collection and analysis may be performed to support the clinical safety assessment, if needed in the event of a safety signal of concern.

Depending on the tolerability profile and safety laboratory results observed in the dose level cohort “n,” one of the following decisions will be made for cohort “n+1”:

- Dose escalation may continue as scheduled.

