#### 9.4.3.2 PHARMACOKINETIC PARAMETERS

For determination of PK parameters, the actual sampling times (taking into account the actual dates and times) will be used. The following PK parameters will be obtained:  $C_{max}$ ,  $t_{max}$ ,  $AUC_{0-t}$ ,  $AUC_{0-\infty}$ , %  $AUC_{0-\infty}$ , CL,  $t_{2/1}$ ,  $\lambda_z$ ,  $V_z$ ,  $V_{ss}$ , and MRT. Individual dose-normalized parameters for  $C_{max}$ ,  $AUC_{0-t}$ , and  $AUC_{0-\infty}$  will also be summarized in terms of dose-normalized  $C_{max}$ ,  $AUC_{0-t}$ , and  $AUC_{0-\infty}$  ( $C_{max,norm}$ ,  $AUC_{0-t,norm}$ , and  $AUC_{0-\infty,norm}$ , respectively). Individual PK parameters of XTMAB-16 will be summarized with descriptive statistics (N, mean, SD, CV, gMean, gCV, median, minimum, and maximum) for each dose.

Dose proportionality will be evaluated for these PK parameters, viz.  $C_{max}$ ,  $AUC_{0-t}$ , and  $AUC_{0-\infty}$  by the power model (PK parameter =  $\alpha \bullet dose^{\beta}$ ). The power model will be fit on the log-transformed linear scale:  $\log(\text{PK parameter}) = \log(\alpha) + \beta \bullet \log(\text{dose})$ . An estimate of unity for  $\beta$  will indicate perfect dose linearity.

Details of the PK analysis, including PK Tables, Listings, and figures, will be provided in the SAP.

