3 INVESTIGATIONAL PLAN

3.1 Overall Study Design and Plan

This is a single-center, randomized, double-blind, placebo-controlled, first-in-human (FIH), single IV infusion of sequential ascending doses of XTMAB-16 in normal healthy male and female participants.

A total of 24 normal healthy adult participants will be enrolled and assigned into 2 treatment cohorts with 12 participants (9 on XTMAB-16 and 3 on placebo) in each cohort as shown in [Table 1](#). Participants will receive a single IV infusion of 2 or 4 mg/kg of XTMAB-16 or placebo on Day 1.

Figure 3-1 Study Design

Abbreviations: FU = follow-up.

Table 1 Dose Cohorts

Cohort	Dose	Escalation Factor	XTMAB-16	Placebo ^a	Total
1	2 mg/kg	-	9	3	12
2	4 mg/kg	2 x	9	3	12

^a The matching placebo will be identical to the XTMAB-16 in terms of volume and infusion duration.

For all cohorts, a sentinel group of 2 participants (1 assigned to XTMAB-16 and 1 assigned to placebo) will be dosed at least 48 hours before the remaining participants in the same cohort. To maintain the treatment blind, study treatment will be prepared by an unblinded pharmacist according to the treatment assignment who will appropriately label the study drug for administration in a way that maintains the treatment blind to clinical research unit (CRU) staff and the participant.

After blinded review of the available safety and laboratory data of the sentinel group by the Principal Investigator (PI), if no notable safety signals are identified, the remaining participants within the same cohort will be dosed. Participants within a cohort should be dosed at least 1 hour apart. If there are no safety concerns, the participants in Cohort 2 will receive XTMAB-16 after at least 14 to 21 days clinical assessment of the participants at Cohort 1.

After a screening period of up to 28 days, participants will be admitted to the CRU on Day -2 for COVID-19 testing and baseline procedures. After confirmation of eligibility, participants will be randomly assigned to treatment (1:1 XTMAB-16 to placebo for sentinel cohort, 4:1 for remaining participants) and administered study drug on Day 1. Participants will remain at the CRU through Day 8 for PK, biomarkers, anti-drug antibody (ADA), and safety assessments, and will be discharged on Day 8 once all procedures for that day have been completed. Participants will return to the CRU on Days 15, 29, 43, 57, and 71 (End of Study/safety follow-up).

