
s.f. = significant figures, d.p. = decimal place

PK Parameter Figures:

The following plots will also be generated:

- Boxplots for dose normalized PK parameters (e.g., C_{max} , AUC_{0-last} , and AUC_{0-inf}) versus treatment

Assessment of Dose Proportionality

- Power Model using ANOVA Method:

An ANOVA of the natural log-transformed PK parameters, ln-transformed dose as a fixed and participant as random effect.

Dose-proportionality based on the power model will be accepted (“not rejected”, in terms of statistical inference) if each of the 95% CIs of the slope of the effect of dose level on each of PK parameters includes 1.

For each of the parameters (C_{max} and AUCs) a plot of the log-transformed PK parameter against the log-transformed dose will be constructed including the fitted line from the linear regression and the line of unity.

Sample SAS Code:

```
ODS OUTPUT lsmeans=lsm estimates=est Diffs=diff1;
```

```
PROC MIXED DATA=PKDATA;
```

```
BY ANALYTE PKPARAM ;
```

```
CLASS SUBJECT;
```

```
MODEL LN_PK= LNDOSE/ddfM=KR;
```

```
RANDOM SUBJECT;
```

```
ESTIMATE "LNDOSE" LNDOSE/CL= 0.05;
```

```
RUN;
```

where:

LN_PK: natural log-transformed PK parameter

LNDOSE: natural log-transformed dose level of <drug>

ANALYTE: analyte (LICO FG-459)

PKPARAM: PK parameter

SUBJECT: participant

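### The SAP declares dose proportionality accepted whenever the slope CIs include 1, so an imprecise result counts as a positive finding

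*SAP*

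**What the plan says.** SAP section 4.10.2, under the assessment of dose proportionality, fits a power model: log PK parameter on log dose, with participant as a random effect. The decision rule reads: "Dose-proportionality based on the power model will be accepted (“not rejected”, in terms of statistical inference) if each of the 95% CIs of the slope" includes 1. Neither document gives limits for the slope interval, a maximum width, or a third outcome between acceptance and rejection.

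The protocol is more restrained. Section 9.4.3.2 says "Dose proportionality will be evaluated for these PK parameters", naming Cmax, AUC0-t and AUC0-∞, and interprets only the estimate: a slope of one "will indicate perfect dose linearity". Section 9.1 plans no hypothesis tests. The acceptance rule therefore appears only in the SAP.

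Each cohort is planned "with 12 participants (9 on XTMAB-16 and 3 on placebo) in each cohort". SAP section 4.5 leaves placebo out of the PK analysis, so at most 9 participants per dose contribute.

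**The concern.** A 95% interval that includes 1 shows that the data are compatible with proportionality. It does not show that the slope is near 1, because the same interval may also include slopes that matter. The bracket in the SAP sentence shows that the authors know the difference, yet the conclusion they prescribe is still acceptance.

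With only two outcomes, imprecision works in favour of the claim: more variable data, or fewer evaluable participants, make acceptance more likely when the true slope differs from 1. The report could then state that proportionality was accepted when the data do not rule out a material departure. Protocol section 2.1 says the "PK results obtained from this study will inform future clinical development", so the label could be carried forward without its interval.

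**Working it through.** The documents give no power, interval width or limits for this analysis, so there is no planned figure to reproduce. I worked out how the rule behaves in the stated design.

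**Inputs from the documents.** Doses 2 and 4 mg/kg (ratio 2); 9 active participants per dose; two-sided 95% CI; all of Cmax, AUC0-last and AUC0-inf must pass.

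**Assumptions.** Between-participant CV of 15% to 50%; correlation of 0.5 to 0.95 between the three parameters; the same CV and slope for all three; log-normal data; all 9 per dose evaluable. With one record per participant, the random participant effect cannot be separated from the residual, so I treated the model as ordinary regression with 16 df.

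**Step 1: precision of the slope.** With two doses, the slope is the difference in mean log exposure divided by ln 2.
- σ = √ln(1 + CV²)
- SE = σ·√(2/9)/ln 2 = 0.680σ
- half-width = t(0.975, 16)·SE = 2.120 × 0.680σ

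At CV 30%, σ = 0.294, SE = 0.200 and the half-width is 0.423. An estimate of exactly 1 then has a CI of 0.58 to 1.42.

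**Step 2: what a slope means for exposure.** Doubling the dose changes dose-normalised exposure by the factor 2^(slope − 1). A slope of 1.5 gives 2^0.5 = 1.41. A ratio of 1.25 corresponds to a slope of 1 + ln 1.25/ln 2 = 1.322, and 0.80 to a slope of 0.678.

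**Step 3: the rule applied jointly.** I simulated 200,000 trials per setting, each parameter with its own pooled variance, accepting when all three CIs include 1. Ranges cover the assumed correlations. The last two columns are for a true slope of 1 and count accepted trials in which a CI reaches a ratio of 1.25 or more, or 0.80 or less.

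| CV | Half-width | Accepted, true slope 1.32 | Accepted, true slope 1.5 | Any CI reaches 0.80 or 1.25 | One named parameter |
|---|---|---|---|---|---|
| 15% | 0.215 | 3–11% | <1% | 37–56% | 27% |
| 20% | 0.286 | 15–31% | 1–4% | 83–96% | 72% |
| 25% | 0.355 | 30–48% | 5–15% | about 98% or more | 93% |
| 30% | 0.423 | 42–60% | 12–28% | >99% | 99% |
| 40% | 0.555 | 59–73% | 31–49% | >99% | >99% |
| 50% | 0.681 | 67–79% | 45–62% | >99% | >99% |

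The rule is not lenient throughout. At a true slope of 1 it accepts in 87–93% of trials, so it fails to accept in 7–13% at every CV, because three intervals must all pass.

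**Step 4: effect of losing participants.** SAP section 4.10.2 can exclude AUC0-inf values, for example for too much extrapolation. For a single parameter at CV 30% and true slope 1.5, the noncentral t distribution gives acceptance of 35% with 9 per dose and 47% with 7. Less information makes the favourable verdict more likely.

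**The case against.** The strongest reply is that the SAP defines its own word: the bracket says that acceptance means non-rejection, so only wording is at issue. That carries some weight, but the bracket does not change the verdict to be reported or add an outcome for an uninformative interval.

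Second, the imprecision will be visible. The sample code requests confidence limits for the slope, and the SAP plans dose-normalised boxplots and log-log plots "including the fitted line from the linear regression and the line of unity". This stands and limits the harm. The rule still gives the spread no influence on the conclusion.

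Third, nothing in the trial depends on the rule. Escalation uses blinded safety data: "The relevant data for this decision should be, at a minimum, AEs, liver and kidney function tests, ECG, blood pressure, and heart rate". The protocol names no use for the accepted label. Mouse exposure "increased in a dose proportional manner in the dose range from 10 to 40 mg/kg", so the departures examined here are scenarios rather than expectations. All of this stands, and it is why the importance is modest.

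Fourth, the size depends on assumptions. That is true: acceptance at slope 1.5 runs from under 1% to 62% across the assumed CVs, and 0.80–1.25 is an outside yardstick. The last two table columns describe interval width when acceptance happens to be correct, not wrong decisions. They still show that the label does not carry the assurance it suggests.

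**Conclusion.** The concern holds. The SAP turns non-rejection into a positive statement, without limits and without an inconclusive result, and goes further than protocol sections 9.1 and 9.4.3.2.

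How often this misleads depends on a CV that the documents do not give. At CV 15–20% the risk of accepting a slope of 1.5 is small (at most about 4%). From CV 20% upward, most accepted results would leave a 25% departure open for at least one parameter even if the drug is perfectly proportional. These figures rest on the assumptions listed with the calculation. The logical fault does not depend on them. The sentence should be changed, but no decision within the trial is at risk.

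**What to change.** Replace the acceptance sentence in SAP section 4.10.2 with text such as:

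> For each parameter, the slope with its 95% CI and the dose-normalised geometric mean ratio r^(slope − 1) with its CI (r being the ratio of the doses given) will be reported as estimates. A CI that includes 1 does not by itself establish dose proportionality.

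If the sponsor wants to make a claim, it should set limits of its own choosing in advance and allow an inconclusive result.

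The cost is one SAP sentence. The slope CI is already estimated, and the ratio is a transformation of it, so no new data or model is needed. The report loses the word accepted.

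A limits-based claim would often end inconclusive at this sample size. As an illustration only, take limits of 0.80–1.25, a 90% CI, one parameter and a true slope of 1. Success is then 84%, 48%, 19% and 6% at CV 15%, 20%, 25% and 30%. By normal approximation, 80% power would need about 14 per dose at CV 20% and 30 at CV 30%. For a first-in-human study with no sample size calculation, reporting estimates is the proportionate choice.

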4.11 Safety Evaluation

All safety summaries and analyses will be based upon the Safety Set. All Safety and tolerability parameters (AEs, laboratory data (hematology, biochemistry, and urinalysis parameters), vital signs, physical exam findings and ECG parameters will be evaluated as following.

4.11.1 Adverse Events

An AE is any untoward medical occurrence in a study participant administered an IMP which does not necessarily have a causal relationship with this treatment.

A treatment-emergent adverse event (TEAE) is defined as an AE that begins or that worsens in severity after at least one dose of the study drug has been administered.

All related TEAEs will be defined as Adverse drug reaction (ADR).

Any AEs with incomplete start and end dates/times will be treated as follows:

- Adverse events with unknown start times, but with start date known, will be imputed with a time of 00:00, unless the start date corresponds to any given dosing date. In this case the start time will be imputed with the time of dosing. If this results in a start date/time after end date/time of the AE, then the time will also be imputed with 00:00.
- Adverse events with completely unknown start dates will be imputed with the date and time of first dosing, unless the end date is known and prior to dosing; in that case the start date will be imputed as the date of Screening and a time of 00:00.
- Adverse events with partially known start dates/times will be treated as follows:
 - If only the day is missing, then the day will be imputed with the first day of the month, unless the month and year in which the AE started is a month and year in which study drug was administered, then the day will be imputed with the first day on which study drug was administered in that month. If this results in a start date after the end date, then the day will be imputed with the first day of the month.
 - If only the month is missing, and the year is a year in which study drug was administered, then the month will be imputed with the first month in which study drug was administered. If this results in a start date after the end date of the AE, then the month will be imputed with JAN. If the known year part is not a year in which study drug was administered, then the month will also be imputed with JAN.
 - If both the day and month is missing and the year is a year in which study drug was administered, then the day and month will be imputed with the day and month of dosing. If this results in a start date after end date, then the day and month will be imputed with 01JAN. If the year is not a year in which study drug was administered, then the day and month will also be imputed with 01JAN.
 - If only the year is missing, then the year will be imputed with the year of dosing.

Unknown dates and times will be shown as NK and NK:NK in the listings (where NK = Not Known), respectively.

Adverse events will be coded using the Medical Dictionary for Regulatory Activities (MedDRA) Version 24.0 or higher.

Unless specified otherwise, all adverse event summaries will include the TEAEs only and adverse event summary counts will be the number of participants reporting adverse events and not the number of events reported.

If more than one event occurred with the same preferred term for the same participant, then the participant will be counted only once for maximum severity level or for most causality level of that preferred term for the summarization of severity or causality accordingly. This table will be sorted alphabetically by SOC and PT.

The following summaries will be presented:

- A table of number (percentage) of participants and number of adverse events with an overview of treatment emergent adverse events (TEAE), severe AEs, ADR, SAE, and AE leading to discontinuation will be presented by XTMAB-16 dose, pooled placebo and overall.
- A table of number (percentage) of participants and number of adverse events with treatment emergent adverse events (TEAE), and SAE summarized by SOC and PT, XTMAB-16 dose, pooled placebo and overall. This table will be sorted by decreasing frequency of the overall column.
- A table of number (percentage) of participants and number of adverse events with TEAEs summarized by SOC, PT, relationship, XTMAB-16 dose, pooled placebo and overall. If more than one event with the same preferred term occurred for the same participant, then the participant was counted only once for that preferred term under the strongest causality. This table will be sorted by decreasing frequency of the overall column.
- Tables of number (percentage) of participants and number of adverse events with TEAEs summarized by SOC, PT maximum severity, XTMAB-16 dose, pooled placebo and overall will be presented. If more than one event occurred with the same preferred term for the same participant, then the participant was counted only once for maximum severity level of that preferred term for the summarization of severity. This table will be sorted by decreasing frequency of the overall column.
- A listing will be created for all Adverse Events (AEs), which will include: treatment received, treatment period, preferred term (PT), system organ class (SOC), AE onset date (and time), AE end date (and time), measure taken on AE, relationship to IMP, AE outcome, severity, frequency, action taken, concomitant medication (if administered), TEAE indicator flag and SAE indicator flag.
- A table of grading of injection site reaction (Table 5) will be summarized by dose cohort and overall.
- A by subject listing of TEAE leading to discontinuation, TEAE expectedness and SAE will be created.

Adverse event summaries will be ordered in terms of decreasing frequency for SOC, and PT within SOC, and then alphabetically for SOC, and PT within SOC.

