#### 9.4.2.2 ADVERSE EVENTS

Safety variables will be analyzed for all study participants in the Safety Set.

Adverse events will be coded by system organ class (SOC) and preferred term (PT) using the Medical Dictionary for Regulatory Activities (MedDRA) version 23 or higher.

The frequency of all AEs during the study will be presented for each cohort and treatment separately by SOC and PT. The data will be displayed as the number of participants experiencing the AEs, percentage of participants, and the number of events.

All TEAEs (defined as those AEs with an onset date/time on or after the start of infusion on Day 1 to end of safety follow-up), serious and nonserious, including deaths, will be tabulated and listed. Laboratory safety parameters that are reported as AEs will also be tabulated and listed.

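### The SAP's missing-month and missing-year rules for AE start dates have no floor at dosing, so a post-dose event can be dated before dosing and leave the TEAE and ADR summaries

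*SAP*

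**What the plan says.** SAP section 4.11.1 has a rule for each kind of incomplete AE start date.

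- **Start date wholly unknown:** "Adverse events with completely unknown start dates will be imputed with the date and time of first dosing", unless a known end date is before dosing.
- **Day missing, in the dosing month and year:** the dosing day is used.
- **Day and month missing, in the dosing year:** the dosing day and month are used.
- **Month only missing, in the dosing year:** "then the month will be imputed with the first month in which study drug was administered". The recorded day stays. The one check is against the AE end date, and its fallback is January.
- **Year only missing:** "If only the year is missing, then the year will be imputed with the year of dosing". No check follows.

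The first three rules anchor the event to dosing. The last two do not.

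The imputed date matters because of the definitions around it. Under the SAP a TEAE "is defined as an AE that begins or that worsens in severity after at least one dose of the study drug has been administered". Protocol section 9.4.2.2 has TEAEs "defined as those AEs with an onset date/time on or after the start of infusion on Day 1 to end of safety follow-up". The SAP defines ADRs as the related TEAEs and states that, unless specified otherwise, "all adverse event summaries will include the TEAEs only".

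**The concern.** The neighbouring rules show a consistent intention: an event that could have begun after dosing is counted as treatment-emergent. SAP section 4.8 takes the same line for medications, which default to concomitant when dates are incomplete. The missing-month and missing-year rules depart from this. They can move a true post-dose onset to before the infusion, while a less complete record of the same event would be counted.

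TEAE incidence is a primary endpoint (SAP section 3.2.1). For post-dose events the error runs one way, because it can only remove them from the summaries. With 9 participants per dose, one lost event can take a preferred term out of a dose column.

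**Working it through.** The documents state no figure to reproduce. The check applies the rules literally to known onset dates. All calendar dates are illustrative, because the documents give no dosing dates.

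**Inputs.** One infusion on Day 1 and follow-up to Day 71 (SAP section 3.1); 9 active participants per dose and 3 placebo per cohort (SAP Table 1); the date rules of SAP section 4.11.1.

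**Single case, month missing.** Dosed 20 July, true onset 5 August of the same year (Day 17).

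- Recorded as 05-NK with the year known: imputed as 5 July, 15 days before dosing, so not a TEAE.
- Adding an end date of 10 August changes nothing, because 5 July is not after it.
- Recorded with day and month both unknown: imputed as 20 July, so a TEAE.

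The end-date check cannot rescue such a case. The dosing month is never later than the month of a same-year post-dose onset, so the imputed start is never later than the true start, and hence never later than the end date.

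**Month missing, by dosing day.** For a given dosing date there are 71 possible onset days. An onset is misplaced when it falls in a later month of the dosing year on a day of the month earlier than the dosing day.

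| Dosed | Day 71 | Misplaced onset days | Share of 71 |
|---|---|---|---|
| 5 July | 13 Sept | 4 + 4 = 8 | 11.3% |
| 15 July | 23 Sept | 14 + 14 = 28 | 39.4% |
| 20 July | 28 Sept | 19 + 19 = 38 | 53.5% |
| 25 July | 3 Oct | 24 + 24 + 3 = 51 | 71.8% |

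**Month missing, averaged over the year.** There are 365 dosing dates × 71 onset days = 25,915 pairs, with no end date recorded. Of these, 9,795 are imputed before dosing.

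- All post-dose onsets: 9,795 / 25,915 = 37.8%.
- Onsets in the dosing calendar year: 25,915 − 2,485 in the following year = 23,430, and 9,795 / 23,430 = 41.8%.
- Extending to Day 78 (nonserious AEs are recorded for 7 further days, protocol section 8.6.4): 10,621 / 28,470 = 37.3%.

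If the recorded year is later than the dosing year, the rule gives January of that later year, which is still after dosing. A further 234 of the 25,915 pairs give a date that does not exist, such as day 31 in a 30-day month. They are not counted as misplaced.

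**Year missing.** An onset after 31 December is moved back a full year. Day 71 first reaches 1 January for dosing on 23 October.

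- Dosed 1 November: 10 / 71 = 14.1%.
- Dosed 1 December: (31 + 9) / 71 = 56.3%.
- Dosed 15 December: (31 + 23) / 71 = 76.1%.

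**Comparison.** The day-missing and the day-and-month-missing rules misplace 0 of 25,915 pairs.

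**Effect of one lost event.** Up to 1/9 = 11 percentage points in a dose column, or 1/6 = 17 points in pooled placebo (3 + 3 = 6).

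**The case against.** The strongest reply is that the trigger hardly arises in this study. Participants are confined from Day -2 to Day 8 and then seen on Days 15, 29, 43, 57 and 71. At each visit the investigator asks about events since the last one (protocol section 8.6.4). Onset is thus bracketed to about 14 days, which with a known day normally fixes the month. Time of onset is a collected item, and missing data go back to the unit for resolution (protocol section 10.1.8). This stands: such dates should be rare.

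Four stronger readings are tempting, and the documents do not support them.

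- **That some 38% or 42% of post-dose events would be lost.** These shares apply only to events with exactly the month missing, a pattern whose frequency is not known. They also assume dosing spread over a year, whereas the study is expected to last 4 to 5 months.
- **That the year rule will misdate events in this trial.** That needs follow-up across 31 December, which the documents neither show nor exclude. A start date 11 months before dosing would also precede consent and should draw a query.
- **That each misplaced event changes a count by 1/9.** A participant counts once per preferred term, so nothing changes in that row if another TEAE carries the same term.
- **That the event disappears from the report.** The all-AE listing keeps it, with unknown date parts shown as NK. Deaths, SAEs and AESIs have their own listing. Protocol section 9.4.2.2 also calls for the frequency of all AEs, although the SAP's default is TEAEs only. A recorded worsening after dosing would still make it a TEAE.

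None of this alters what the two rules do when they apply.

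**Conclusion.** The point holds as a minor defect. Two of the partial-date rules can date a post-dose AE before dosing, in conflict with the adjacent rules for less complete dates. For the missing-month pattern the share misplaced depends on the dosing day: 11% for dosing on 5 July, 39% on the 15th and 72% on the 25th. These figures assume onset uniform over Days 1 to 71; the yearly averages also assume dosing dates uniform over the year. The expected number of affected events is probably small, though the documents allow no estimate of it. The case for a change is that the rule gives a wrong result in the non-conservative direction for a primary safety endpoint with small columns, and that correcting it costs very little.

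**What to change.** Add one sentence to both the missing-month and the missing-year bullets of SAP section 4.11.1:

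*If the imputed start date is before dosing, and the known date parts and the end date do not exclude onset on or after dosing, impute the start as the date and time of dosing, so that the event is counted as treatment-emergent.*

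By construction, no true post-dose onset would then be moved before dosing under either rule. An event whose end date or known date parts place it before dosing stays there.

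The cost is one SAP sentence and about one line of derivation code, with no change to data collection or endpoints. If the SAP is already final, the change goes through the modification form named in SAP section 1. The downside is that an occasional pre-dose event with a partial date will be counted as a TEAE, which is the conservative direction the adjacent rules already take.
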